8.3.5 ADVERSE EVENT REPORTING

See 8.3.4.

8.3.6 SERIOUS ADVERSE EVENT REPORTING

See 8.3.4.

8.3.7 REPORTING EVENTS TO PARTICIPANTS

Not applicable

8.3.8 EVENTS OF SPECIAL INTEREST

Not applicable

8.3.9 REPORTING OF PREGNANCY

Not applicable

8.4 UNANTICIPATED PROBLEMS

8.4.1 DEFINITION OF UNANTICIPATED PROBLEMS

This protocol uses the definition of Unanticipated Problems as defined by the Office for Human Research Protections (OHRP). OHRP considers unanticipated problems involving risks to participants or others to include, in general, any incident, experience, or outcome that meets all of the following criteria:

- Unexpected in terms of nature, severity, or frequency given (a) the research procedures that are described in the protocol-related documents, such as the Institutional Review Board (IRB)-approved research protocol and informed consent document; and (b) the characteristics of the participant population being studied;
- Related or possibly related to participation in the research (“possibly related” means there is a reasonable possibility that the incident, experience, or outcome may have been caused by the procedures involved in the research); and
- Suggests that the research places participants or others at a greater risk of harm (including physical, psychological, economic, or social harm) than was previously known or recognized.

8.4.2 UNANTICIPATED PROBLEMS REPORTING

Unanticipated Problems that are unexpected, related or possibly related to this research (including anywhere there is a reasonable possibility that the incident or outcome may have been caused or associated with the study) and that suggests that the research places clinicians or patients at greater risk of harm than was previously known or recognized will be thoroughly and promptly investigated. The Unanticipated Problem will be investigated, formally written down with a corrective plan and measures to prevent reoccurrence. This report will be shared with the NIA Program Officer and Safety Officer within 48 hours of study's knowledge of the problem.

8.4.3 REPORTING UNANTICIPATED PROBLEMS TO PARTICIPANTS

Not applicable

9 STATISTICAL CONSIDERATIONS

9.1 STATISTICAL HYPOTHESES

Milligram morphine equivalents in prescriptions filled daily by patients of letter recipients will decrease following receipt of letter as compared to baseline.

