1 PROTOCOL SUMMARY

1.1 SYNOPSIS

Title:	Comparative Effectiveness of Two Letters to Encourage Judicious Prescribing of Opioids: A County-wide Project in Los Angeles
Grant Number:	P30AG024968
Study Description:	In collaboration with the Los Angeles County Medical Examiner's Office and the State of California's controlled Substance Utilization Review and Evaluation System (CURES), the investigators propose to review opioid poisonings over 12 months and send letters to prescribers in California when at least one of the provider's prescription(s) was filled by a patient who died of an opioid poisoning in Los Angeles County. The letters will be non-judgmental and factual, explaining that a patient of the provider who was being treated with prescription narcotics died of an opioid poisoning. The letters will also encourage judicious prescribing including use of the CURES system before prescribing. The investigators will evaluate physician prescribing practices over 24 months (12 months pre- and 12 months post-letter) using data from the CURES database. The hypothesis is that letters will make the risk of opioids more cognitively available and that physicians will respond by prescribing opioids more carefully, resulting in fewer deaths due to misuse and more frequent use of the CURES system.
Objectives*:	
1) To conduct a randomized trial comparing two versions of a letter sent to prescribers in Los Angeles County notifying them that one of their prescriptions was filled by a patient who died of an opioid poisoning, and2) Evaluate the effects of the randomized trial and identify factors that predict intervention effectiveness.
Endpoints*:	
1) Average change over time in Milligram Morphine Equivalents (MME) dispensed2) Average change over time in Benzodiazepine Equivalents (BE) dispensed
Study Population:	Los Angeles County prescribers
Phase* or Stage:	IV
Description of Sites/Facilities Enrolling Participants:	Los Angeles County Medical Examiner's Office

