4 STUDY DESIGN

4.1 OVERALL DESIGN

This is a decedent-cluster randomized field experiment; clusters of prescribers within each decedent will be randomly allocated to one of two letters interventions. This design avoids treatment contamination—clinicians prescribing to the same patient will be able to share information about the intervention without diluting its effect. If two or more decedents have the same prescriber, that prescriber will be assigned to one and only one of those decedent clusters by random draw. Two factors will serve as random strata: 1) whether the decedent received a prescription from a clinician with a single or multiple deaths, and 2) whether opioids only, opioids in combination with benzodiazepines, or benzodiazepines only were the cause of death. The first strata are designed to form equivalent groups on prescriber risk posture. The second strata equate preference for type of scheduled drug prescribed in practice. Strata will be crossed to form $2 \times 3 = 6$ randomization groups.

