6.3 MEASURES TO MINIMIZE BIAS: RANDOMIZATION AND BLINDING

For randomization, two decedent lists will be generated from the crossed strata levels. Using random.org’s sequence generator, two true random integer sequences derived from atmospheric noise will determine decedent order in each list. For each ordered list, prescribers to decedents in the first half will receive Letter A, the second half of the list will receive Letter B.

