9.4 STATISTICAL ANALYSES

9.4.1 GENERAL APPROACH

We will convert opioids to milligram morphine equivalents (MME) using formulas published by the CDC.²⁹ Descriptive and inferential statistics will be carried out in STATA (Version 14.0; Stata Corporation, College Station, TX). The *cmp* command in STATA will be used to compute a difference in differences estimator within a mixed-model censored linear regression.³⁰ The difference in differences estimator compares the average change over time in MME dispensed for prescribers in the group receiving letter version A, compared to the average change over time for those prescribers in receiving version B. To ensure normally distributed data, we evaluate the natural log of MME. Censored regression has a continuous component and a discrete one. The natural log MME doses estimated over days where opioids were dispensed in the name of a prescriber represent the continuous part, and days with no opioids filled in that prescriber's

name represent the discrete part of the model. We denote estimation of the dependent variable as $\log(\widehat{MME})$ * to distinguish it from uncensored estimation. The analysis is represented by:

$$\log(\widehat{MME}) *_{ijk} = \beta_1 x_{1ij} + \beta_2 x_{2ij} + \beta_3 x_{3ij} + \delta_{i(k)} \quad [1]$$

where β_1 , β_2 and β_3 are fixed effects coefficients on time, x_1 , intervention, x_2 , and time by intervention interaction, x_3 , respectively. Alphabetic subscripts describe the i th prescriber, j th prescription filled and k th decedent, the nested random intercept $\delta_{i(k)}$ is normally distributed with mean zero and variance, $\sigma_{i(k)}^2$, for each i prescriber nested in (i.e., having prescribed to) decedent k , $i(k)$. With natural log transformed data, the value $100 \cdot [\exp\{\beta_3\} - 1]$ measures precisely the percentage change in MME attributable to the intervention when data are uncensored (see Woolridge (2008), pp. 212 and 410).

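### Section 9.1 states the hypothesis as a before-to-after fall among letter recipients, which is not the Letter A versus Letter B contrast that the trial randomises

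*Combined protocol and SAP*

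**What the plan says.** The only entry under Statistical Hypotheses (9.1) reads: "Milligram morphine equivalents in prescriptions filled daily by patients of letter recipients will decrease following receipt of letter as compared to baseline". It is directional, compares recipients with their own baseline, and names neither letter.

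The design is a comparison of letters. The first objective in the synopsis (1.1) is "To conduct a randomized trial comparing two versions of a letter sent to prescribers in Los Angeles County". Section 4.1 says that "clusters of prescribers within each decedent will be randomly allocated to one of two letters interventions", and 6.3 says that "prescribers to decedents in the first half will receive Letter A, the second half of the list will receive Letter B". Sections 5 and 5.5 extend the intervention to all eligible clinicians, so nobody is left without a letter.

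The analysis follows the design. The difference-in-differences estimator in 9.4.1 "compares the average change over time in MME dispensed for prescribers in the group receiving letter version A" with the corresponding change under version B. The effect is read from β3, the time-by-intervention coefficient, through 100·[exp(β3) − 1], which is said to be what "measures precisely the percentage change in MME attributable to the intervention when data are uncensored". Section 9.2 sizes the trial per arm with a two-tailed 5% test.

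Other passages fit less well. Section 10.1.6 describes the study as having one arm. Sections 8.2, 8.3.3.3 and 9.4.4 compare letter recipients with controls. Under 9.4.2, the primary analysis, only the heading is visible.

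**The concern.** A reader who wants to know whether the trial met its hypothesis will go to 9.1. The quantity named there, change from baseline among all recipients, has no concurrent comparator in this trial. Random allocation balances the two letter groups against each other; it gives no information on what recipients would have prescribed without any letter.

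What is at stake is the conclusion drawn. Judged by 9.1, a general decline in prescribing would count as success and could be read as showing that the letters work. Judged by the randomised contrast, the same data would show no difference between letters. The opposite error is also possible: one letter is better, but 9.1 is not met because prescribing did not fall overall.

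**Working it through.** The plan has no figure to reproduce on this point. Section 9.1 gives no expected size, and the 103 decedents per arm in 9.2 is not used here. The check is algebraic.

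**Inputs.** The hypothesis is from 9.1, the two arms from 4.1 and 6.3, the absence of a no-letter group from 5 and 5.5, the estimator from 9.4.1, and the sidedness and alpha from 9.2.

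**Step 1: write the change in each arm.** On the log MME scale, let S be the mean change from baseline to follow-up that would occur with no letter, and let L_A and L_B be the added effects of the letters. Then

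- change under A: D_A = S + L_A
- change under B: D_B = S + L_B

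S is the same in both arms in expectation because decedent clusters are allocated at random.

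**Step 2: the quantity in 9.1.** Weighting the arms equally, the mean change among recipients is S + (L_A + L_B)/2. If 9.1 is instead read arm by arm, the quantities are S + L_A and S + L_B. S remains in either reading, and no group in the trial estimates S alone.

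**Step 3: the quantity in 9.4.1.** D_B − D_A = L_B − L_A. S cancels. This is β3 if Letter B is the arm coded 1; the sign reverses otherwise.

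**Step 4: compare the two.** For any c > 0:

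| Situation | S | L_A | L_B | Change in A | Change in B | Mean change (9.1) | B minus A |
|---|---|---|---|---|---|---|---|
| Both letters work equally | 0 | −c | −c | −c | −c | −c, met | 0 |
| Neither works, prescribing falls anyway | −c | 0 | 0 | −c | −c | −c, met | 0 |
| Only B works, background rise | +c | 0 | −2c | +c | −c | 0, not met | −2c |

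The first two rows give the same data. In both, 9.1 is met and the planned effect is 100·[exp(0) − 1] = 0%. In the third row 9.1 is not met for recipients as a whole, although the letters differ by 2c.

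**Step 5: link to the model.** Section 9.4.1 says only that the three coefficients "are fixed effects coefficients on time", intervention and their interaction. If time and letter are both 0/1 indicators (an assumption), 9.1 concerns β1 in one arm and β1 + β3 in the other, while the randomised contrast is β3 alone. Steps 1 to 4 do not depend on that coding.

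**Step 6: look for text that overrides 9.1.** Section 9.4.1 describes an estimator but does not name its test as the deciding one. Section 9.4.2, where that would belong, shows only its heading. No visible text replaces the hypothesis in 9.1.

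**The case against.** The strongest reply is that the plan already states the right contrast everywhere that governs the analysis. The title and first objective compare two letters, randomisation is A versus B, 9.2 is two-tailed and per arm, and 9.4.1 defines the estimator as change under A against change under B. This stands. A reader might infer from 9.1 that the planned analysis is itself uncontrolled, or that the sponsor intends to declare success on a pre-post test. The documents support neither: no pre-post significance test is planned, and 9.2 and 9.4.1 are not at fault here.

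Second, 9.1 may express only a scientific expectation. That reading suits the synopsis, where "The hypothesis is that letters will make the risk of opioids more cognitively available and that physicians will respond by prescribing opioids more carefully" describes a mechanism and can stay. It does not suit a sentence that is the sole entry under Statistical Hypotheses.

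Third, the control arm of the earlier San Diego trial barely moved (0.1, interval −2.8 to 3.2, section 2.1), so pre-post change might be thought safe. That is another county and an earlier trial, and cannot serve as a concurrent control. Equally, its interval limits express sampling uncertainty and are not estimates of drift in Los Angeles, so they do not show that a pre-post reading would be biased by any given amount.

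Fourth, the mentions of controls might suggest an undescribed no-letter group, and the one-arm phrase might suggest that the sponsor sees the study as pre-post. Sections 4.1, 5 and 6.3 leave no room for a no-letter group. The one-arm phrase is a single remark under safety oversight and is weak evidence of intent.

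Finally, the bare heading at 9.4.2 may reflect text lost when the PDF was converted. That cannot be excluded.

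**Conclusion.** The point holds as a mismatch between the stated hypothesis and the randomised comparison. As written, 9.1 can be met with β3 = 0 and can fail with β3 ≠ 0, and meeting it would not show that the letters work. This is more than a matter of style, because 9.1 is the only stated criterion and it supports a conclusion that the design cannot give. It is less than a fault in the analysis, because the described estimator is the right one.

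No magnitude is attached: the documents give no background change for these prescribers. The conclusion rests on three things: there is no no-letter group (5, 5.5, 4.1, 6.3); background change is the same in both arms in expectation; and no text missing from 9.4.2 already names the A-versus-B test. If such text exists, the point reduces to correcting 9.1 to agree with it. The role of benzodiazepine equivalents and the coding of time are separate questions, and the point does not depend on them.

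**What to change.** 1. In 9.1, state H0: β3 = 0, that is, no difference between Letter A and Letter B in change in log MME from baseline to follow-up, tested two-sided at the 5% level already used in 9.2.
2. In 9.4.2, name the test of β3 as the primary test for MME.
3. State that within-arm change from baseline will be reported descriptively and not as evidence that the letters work.
4. Reconcile the one-arm description in 10.1.6, and the controls in 8.2, 8.3.3.3 and 9.4.4, with a design of two randomised letter arms, and say which groups the safety comparison is between.

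The synopsis statement of mechanism may remain as a scientific expectation.

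For the primary MME test the cost is wording only: no new data are needed, and the interaction term is already in the model. The real price is in what can be claimed. The sponsor gives up a pre-post effectiveness conclusion, and a null β3 will not show whether both letters work or neither does.

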9.2 SAMPLE SIZE DETERMINATION

We calculated the sample size needed to detect an effect of the letter intervention using standard formulas for power analysis in cluster randomized trials and the 'clusterPower' package in R statistical computing language. For this calculation we used data on decedents and prescribers at the San Diego County Medical Examiner between January 1 and December 31, 2013 published in Lev et al. 2016 and Doctor et al. 2018. We assume a two tailed test with a 5% Type I error rate and an 80% chance to detect an effect. Doctor et al. (2018) found mean of 5.5 prescribers for each decedent. Coefficient of variation we assume to be 1.22, which implies that 99% of decedents had 20 or fewer prescribers in the year before their death. We assume a 50% reduction in mean difference as compared to the effect reported in Doctor et al. 2018 and a standard deviation of +140 daily MME within cluster. Most clinician clusters for process measures have intracluster correlations that fall between 0.05 and 0.15. We assume a more conservative intracluster correlation of 0.2; in our design we randomized by decedent to reduce intracluster correlation. We utilized the Taylor method for calculating variance inflation due to unequal cluster sizes. Under these assumptions, we would need 103 decedents per study arm; given annual opioid overdose frequency in Los Angeles, we expect to have 192 per arm. We have ample power to detect an effect.

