2 INTRODUCTION

2.1 STUDY RATIONALE

One promising strategy for changing physician behavior is through use of “nudges”. The term “nudge” identifies a set of social and cognitive devices that persuade decisions in subtle ways while preserving choice. When prescribing narcotics, physicians may not have recent experiences that come to mind as to why these drugs are dangerous, making risks seem remote. They may also not consult data on a patient’s other narcotic prescriptions in their State’s pharmaceutical drug monitoring program. One useful nudge capitalizes on a finding called “Availability”. Availability is the notion that people rely upon knowledge that is salient, recent and readily available to them to evaluate risks and make decisions. If a physician issued a prescription for a narcotic that resulted in a recent opioid poisoning, providing that physician with this feedback may make the physician more likely to consult a pharmaceutical drug monitoring program database and also prescribe more judiciously.

We published a randomized trial in the journal *Science* demonstrating that carefully crafted letters, supportive in tone and designed to increase the availability of patient harms, are effective in reducing opioid prescribing among high risk prescribers (i.e., those with a death in their practice).⁹ Milligram morphine equivalents in prescriptions filled daily by patients of letter recipients compared to controls decreased by 9.7% (95% confidence interval: 6.2 to 13.2%; $p < 0.001$) over a 3-month period following intervention (Figure 2). We also observed both fewer high dose prescriptions and new patients started on opioids among letter recipients. Learning of a patient's fatal overdose may instill safe opioid prescribing habits in physicians.

Figure 2. Adjusted milligram morphine equivalent prescriptions

Parameter	Randomization group	
	Letter	Control
Prescribers followed	388	438
Preintervention	72.5 (71.3 to 73.7)	71.6 (70.3 to 72.8)
Postintervention	65.7 (63.8 to 67.5)	71.7 (70.0 to 73.5)
Increment (pre- to post-)	-6.8 (-9.9 to -3.8)	0.1 (-2.8 to 3.2)
Difference in increment	-6.9 (-13.1 to -1.0)	
P value	0.001	

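### Section 9.2's 103 decedents per arm does not follow from its inputs: a standard deviation of 140 MME needs about 14,000 per arm and leaves about 6% power at the expected 192

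*Combined protocol and SAP*

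**What the plan says.** Section 9.2 (Sample Size Determination) is the protocol's sample size calculation. It opens: "We calculated the sample size needed to detect an effect of the letter intervention". The test and power are set by "We assume a two tailed test with a 5% Type I error rate and an 80% chance to detect an effect". The effect is set by "We assume a 50% reduction in mean difference as compared to the effect reported" in the earlier San Diego trial, and the spread by "a standard deviation of +140 daily MME within cluster". The other inputs are a mean of 5.5 prescribers per decedent, a coefficient of variation of cluster size of 1.22, an intracluster correlation of 0.2, and the Taylor method for unequal clusters. The result is "Under these assumptions, we would need 103 decedents per study arm". With 192 per arm expected, the section closes: "We have ample power to detect an effect".

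The size of the earlier effect is in Section 2.1, Figure 2: a difference in increment of -6.9 daily MME (95% interval -13.1 to -1.0) between 388 prescribers sent a letter and 438 controls who were not. The letter arm's own change was -6.8.

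**The concern.** The ratio of effect to spread is out of proportion to the stated sample size. An effect of 3.45 against a standard deviation of 140 is a standardised difference of 3.45 / 140 = 0.025. No two-arm trial with about a hundred clusters of five or six prescribers can detect that.

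The effect is also borrowed from a different contrast. The earlier trial compared a letter with no letter. Here every prescriber receives a letter (Sections 4.1 and 6.3), the estimator in Section 9.4.1 compares version A with version B, and version B differs by a short added text (Section 4.3). Section 9.2 gives no reason to expect that text to produce half of the whole earlier letter effect.

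The stake is how the result is read. If A and B do not differ significantly, a statement of ample power invites the conclusion that the letters are equivalent. The printed inputs would not support that conclusion.

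**Working it through.** **Inputs.** Effect d = 6.9 / 2 = 3.45 (Section 2.1, Figure 2; halving from Section 9.2). From Section 9.2: SD = 140, m = 5.5, CV = 1.22, ICC = 0.2, two-sided 5%, 80% power, so (1.960 + 0.842)² = 7.849. Allocation is 1:1 (Section 6.3). I first take 140 as the total SD.

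**Variance inflation (Taylor).**
- L = m·ICC / (1 + (m − 1)·ICC) = 1.1 / 1.9 = 0.579
- VIF = 1.9 / (1 − 1.22² × 0.579 × 0.421) = 2.98
- For comparison, the weighted formula gives 1 + ((1 + 1.22²) × 5.5 − 1) × 0.2 = 3.54, and equal clusters give 1.90.

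**Attempt to reproduce 103.** Decedents per arm = 2 × 7.849 × SD² × VIF / (d² × m).

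| Reading of the inputs | Decedents per arm |
|---|---|
| SD 140, d 3.45, Taylor (as printed) | 14,015 |
| SD 140, d 3.45, weighted inflation | 16,625 |
| SD 140, d 3.45, equal clusters | 8,930 |
| SD 140 strictly within cluster (total variance 140²/0.8), Taylor | about 17,500 |
| SD 140, full effect 6.9, equal clusters | about 2,230 |
| Variance 140, d 3.45, Taylor | 100.1 (normal), 101.1 (t) |
| Variance 140, d 3.40, Taylor | 103.1 (normal), 104.0 (t) |

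The effect of 3.40 is half of the letter arm's own change of 6.8. Solving backwards, 103 per arm needs an SD of 12.0 at d = 3.45 or 11.8 at d = 3.40, and √140 = 11.8.

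**Without any clustering.** 2 × 7.849 × 140² / 3.45² = about 25,850 prescribers per arm, against 192 × 5.5 = 1,056 expected. The clustering method therefore cannot explain the gap.

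**Power at 192 per arm, SD 140.**
- SE = √(2 × 140² × 2.98 / 1,056) = 10.52
- Power = Φ(3.45/10.52 − 1.96) + Φ(−3.45/10.52 − 1.96) = 0.051 + 0.011 = 6.2% (6.0% with VIF 3.54)
- Difference detectable with 80% power = 2.802 × 10.52 = 29 MME per day (32 with VIF 3.54), or 41% to 45% of the mean of about 72 in Figure 2.

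**Power at 192 per arm, variance 140.** SE = 0.889, power is about 97%, and the detectable difference is 2.5 MME per day. That is 36% of the entire earlier letter effect (2.5 / 6.9), required as a difference between two letters.

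**Rough check against Figure 2.** This assumes independent prescribers and takes SE as interval width / 3.92. Requirements use d = 3.45 and Taylor inflation.

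| Figure 2 row | Implied SD | Decedents per arm | Power at 192 |
|---|---|---|---|
| Pre-letter levels | 12 to 13 | near the variance-140 result at the lower end | – |
| Post-letter levels | about 19 (18.6 used) | about 248 | 69% |
| Increments | 31 to 32 | about 690 to 730 | 30% to 32% |
| Difference in increment | about 44 | about 1,400 | 18% |

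These are assumption-based ranges, not inputs of the plan. Of these rows, only the pre-letter levels are compatible with 103 per arm.

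**The case against.** The strongest reply is that 140 is simply a mislabelled variance. On that reading the requirement is 100 to 104 and power at 192 is about 97%, so the documents do not prove that the trial has 6% power. This stands: 6% is what the printed inputs imply, not an established property of the trial. Figure 2 points the same way. A prescriber-level SD of 140 with 388 and 438 prescribers would give a 95% half-width of about 19 MME even without clustering, against about 6 reported. But the variance reading is an inference from arithmetic. At the stated effect of 3.45 it gives 100 or 101, and reaching 103 takes 3.40. The figure 140 might instead be a day-level SD that averaging over days would reduce. Section 9.2 says neither, and it does not show where 140 comes from.

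Section 9.4.1 plans repeated daily data in a log-scale difference-in-differences model, which may gain precision. Section 9.2 works in raw MME and claims no such gain, so the model cannot account for the stated 103.

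Figure 2 is a weak base for back-calculation. Its interval implies z = 6.9 / 3.09 = 2.24 and p of about 0.025, but 0.001 is printed. That is a reason to show the whole range rather than one row. It does not rescue the calculation.

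Enrolment follows largely from a County programme that writes to every eligible prescriber (Sections 5 and 5.5). So the error changes what may be claimed about power, not how many are enrolled. Finally, the choice of effect is a matter of judgement rather than arithmetic and stands apart from the question about 140. It is kept here because the same paragraph must be rewritten and the detectable difference has to refer to the contrast being tested.

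**Conclusion.** The concern holds. Taking the inputs as printed, with 140 as the total SD and the effect as half of Figure 2's 6.9, Section 9.2 needs about 14,000 decedents per arm rather than 103, a factor of about 136, and 192 per arm gives about 6% power. No variant tried with an SD of 140 needs fewer than about 2,230 per arm. The printed SD and the stated sample size cannot both be right. If 140 is a variance, the number and the power claim survive for a difference of 3.45. If it is an SD, both fail. Under either reading, the power statement concerns an effect scaled from letter versus no letter, while the trial tests letter A against letter B.

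**What to change.** Rerun Section 9.2 and restate it:

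1. Say whether 140 is a standard deviation or a variance, whether it is total or within cluster and per prescriber or per day, and give its source.
2. State the effect as a number (3.45 or 3.40) and where it comes from.
3. If 140 is a variance, print it as variance 140 (SD 11.8) with the resulting number per arm. If it is an SD, replace 103 and the claim of ample power with what follows: about 6% power and a detectable difference of 29 to 32 MME per day at 192 per arm.
4. In either case, express power as the detectable letter A versus letter B difference at 192 per arm, and say why a difference of that size is plausible for the added text.

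The cost is one rerun and a rewritten paragraph, with no extra enrolment or design change. The stated power may become much less favourable, depending on the answer to item 1.
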